HIPAA	Health Insurance Portability and Accountability Act of 1996
ICF	Informed Consent Form
ICH	International Conference on Harmonisation
IEC	Independent Ethics Committee
IRB	Institutional Review Board
IM	Intramuscular
IN	Intranasal
IT	Information Technology
IUD	Intrauterine Device
IV	Intravenous
MAD	Mucosal Atomization Device
OS	Operating System
PI	Principal Investigator
SAE	Serious adverse experience
SID	Subject Identification Number
SC	Subcutaneous
SQL	Structured Query Language
SSL	Secure socket layer
UCSF	University of California – San Francisco
VPN	Virtual private network

PROTOCOL SYNOPSIS

TITLE	OPIATE WITHDRAWAL RESPONSES TO INTRANASAL NALOXONE AS AN INDEX OF ALTERED ENDOGENOUS OPIOID ACTIVITY AMONG WOMEN WITH OBESITY: A FEASIBILITY AND EFFICACY STUDY
SPONSOR	[name]
FUNDING ORGANIZATION	National Heart Blood and Lung Institute (NHLBI)
NUMBER OF SITES	1
RATIONALE	Understanding what drives compulsive overeating among individuals with obesity will lead to the development of more effective treatments. A large body of literature implicates the endogenous opioid system in eating behavior. Researchers have published the use of exogenous opioidergic blockade as a method to assess endogenous opioid activity in obesity ^{1,2} . Data suggest that women are more sensitive to exogenous opioidergic blockade. Our work shows that withdrawal responses, as indexed by nausea following opioidergic antagonism using oral naltrexone, are associated with non-homeostatic eating in obese women ^{1,2} . To (1) reduce the amount of time needed to investigate associations between eating behavior, obesity, and the endogenous opioid system, thereby reducing subject burden, and (2) take the initial steps toward the development of a cost-and time-effective method to assess endogenous opioid activity in women, we plan to evaluate the use of naloxone hydrochloride administered intranasally (intranasal naloxone).
STUDY DESIGN	This is a single-center, double-blind, placebo-controlled, randomized, crossover trial design.
PRIMARY OBJECTIVE	1. To determine if 2 mg/2 mL intranasal naloxone elicits the withdrawal symptom of nausea (present versus absent) in obese women.
SECONDARY OBJECTIVES	1. To determine if 2 mg/2 mL intranasal naloxone elicits other withdrawal symptoms, as measured by subjective opiate withdrawal scales ³ in obese women 2. To determine the rate of the cortisol response following 2 mg/2 mL intranasal naloxone in obese women
NUMBER OF SUBJECTS	24 women
SUBJECT SELECTION CRITERIA	
Inclusion Criteria:
 
 1. Subject must be able to complete written informed consent procedures and be able to comply with the requirements of the study. 2. Women aged 18 years or older 3. Obese, as defined by BMI greater than or equal to 30

	
4. Self-reported binge eating as defined in DSM-5, in the last 4 weeks
 
5. If sexually active with men and pre-menopausal, must agree to use birth control (e.g., barrier methods, oral contraceptive)
 
6. Must have negative pregnancy test at visit 1
 
Exclusion Criteria:
 
 1. Presence of a condition or abnormality that in the opinion of the Investigator would compromise the safety of the subject or the quality of the data 2. Pregnant or breastfeeding 3. Known hypersensitivity to naloxone hydrochloride or to any ingredients in naloxone hydrochloride 4. Allergies to any ingredients in naloxone hydrochloride 5. History of or current alcoholism 6. History of or current drug dependence 7. Bulimia Nervosa as defined in DSM 5 8. Current or past use of opiate-containing medications in the last 30 days 9. Plan to use opiate-containing medications during the study days 10. Use of opiate medications or drugs, which are contraindicated with naloxone hydrochloride 11. Medical conditions that are contraindicated with intranasal procedures: Nasal septal abnormalities, nasal trauma, epistaxis, excessive nasal mucus, and intranasal damage caused by the use of substances (e.g., cocaine) 12. Severe hypotension (<90/60 mmHg) 13. Recent or current use of vasoconstrictor or vasodilator medications 14. Current or history of diabetes
TEST PRODUCT, DOSE, AND ROUTE OF ADMINISTRATION	2 mg/2 mL Naloxone Hydrochloride (Intranasal Naloxone) 1 mg/1 mL administered per nostril using a nasal mucosal atomization device (MAD) (manufactured by Teleflex, Inc., Research Triangle Park, NC, USA).
CONTROL PRODUCT, DOSE AND ROUTE OF ADMINISTRATION	2 mL 0.9% sodium chloride (Intranasal Placebo) 1 mL administered per nostril using a nasal mucosal atomization device (MAD) (manufactured by Teleflex, Inc., Research Triangle Park, NC, USA).
DURATION OF SUBJECT PARTICIPATION AND DURATION OF STUDY	Subjects will be in the study for up to 3 weeks. There will be a period of at least 24 hours between visits 1 and 2. Web-based eligibility: Screening for self-report eligibility criteria, approx. 15 minutes Phone Screen: Phone call to review eligibility and schedule visit 1, planning for visit 1, approx. 15 minutes Visit 1: In-person baseline assessment (screening for pregnancy and

	drug use), approx. & Administration day 1 (approximately 1.5-2 hours) Visit 2: Administration day 2 (approximately 1.5-2 hours) Recruitment and participation are expected to take 6 months
CONCOMITANT MEDICATIONS	
Allowed:
 
 1. Medications are permitted with use of naloxone hydrochloride unless listed below under “prohibited” 
Prohibited:
 
 1. Current use of opiate-containing medications 2. Current use of vasoconstrictor medication 3. Initiation of new medications that are contraindicated with naloxone hydrochloride use during the study period 4. Current use of insulin
EFFICACY EVALUATIONS	
 1. Self-reported nausea at 0 minutes (pre-administration), and 10 and 30 minutes following administration of test product or control product 2. Self-reported symptoms of withdrawal as measured by the subjective opiate withdrawal scale (SOWS³) at 0 minutes (pre-administration), and 10 and 30 minutes following administration of test product or control product 3. Salivary cortisol values at 0 minutes (pre-administration) and 20 and 50 minutes following administration of test product or control product
PRIMARY ENDPOINT	
 1. Presence or absence of the self-reported withdrawal symptom of nausea following administration of the test versus control product.
SECONDARY ENDPOINTS	
 1. Scores on self-report Subjective Opiate Withdrawal Scale (SOWS)³ following administration of the test versus control product. 2. Rate of the cortisol response, as measured by salivary cortisol, following administration of the test versus control product.
OTHER EVALUATIONS	N/A
SAFETY EVALUATIONS	Incidence of unexpected adverse events. Subjects will be monitored for unexpected adverse events and serious adverse events following administration of the test product and control product.
PLANNED INTERIM ANALYSES	Due to the current study design and safety profile of this test product, no interim analyses are planned.
STATISTICS Primary Analysis Plan	McNemar's tests will be performed to evaluate whether there is a statistically significant difference in nausea response (dichotomously scored as present or absent) across test product (intranasal naloxone) and control product (intranasal placebo) conditions.

Rationale for Number of Subjects	We do not expect any nausea responses to the control product, just as we typically do not expect side effects from placebos. Under the null hypothesis of no difference between conditions, we would also expect no nausea responses under the alternative hypothesis. In terms of probability, “no responses” implies a probability of 0: In other words, an impossible event. A single nausea response to the test product would decisively refute the null. But nausea responses, under either condition, are not literally impossible. We have therefore powered against the expected value of 0 by using the beta distribution with $r = 0$ as a Bayesian prior, in place of the usual point value. The beta with $r = 0$ is a U-shaped distribution concentrating most of the density on the extreme values. Specifically, for values of p from .01 to .99, in .01 increments, we calculated the ordinate of the beta distribution with trial values of N ; calculated the one-tailed rejection region (outcomes of fewer than 0 nausea responses were not considered) for that value of p and N ; calculated the power for that N and an alternative value of p (e.g., .4); then used the corresponding ordinate for each value of p as a weight, and calculated the average across the range from .01 to .99 as our estimate of power. Since nausea responses are not literally impossible, we also explored power with null proportions up to .3, with the alternatives in the below table. For these nonzero values, a standard binomial power analysis would have sufficed, but for consistency we have used the corresponding Bayesian priors. The beta prior with $r = N/10$, for example, will concentrate probability on values near .1, whereas that with $r = 0$ will concentrate it around 0. The latter, approximating the impossible event, of course yields high power, whereas power declines as the binomial becomes more symmetrical. For the values of potential interest to us, an N of 24 will suffice for 80%+ power. (Following from the above rationale, the entries in the table below do not correspond to standard power calculations for the McNemar test. The test for 0% vs. 40%, for example, is a test of whether the percentages for the two populations are both 20%; the power of this test is just 1 of 99 values averaged, with weights from the beta distribution, for the results in the table below).			
% Endorsing Nausea	Number Needed (N)	Power to detect difference		
Control Product	Test Product			
0%	20%	20	.811	
0%	30%	12	.823	
0%	40%	9	.844	
10%	40%	16	.817	
20%	50%	21	.805	
30%	60%	24	.805	

Reference: Uebersax, J.S. Bayesian unconditional power analysis (2007).

1 BACKGROUND

Opioid antagonists, such as intravenously and intranasally delivered naloxone (brand name: Narcan), are used clinically throughout the US to acutely reverse opiate drug overdose⁴⁻⁶. A nasal naloxone spray device was recently approved for opioid overdose: <http://www.fda.gov/NewsEvents/Newsroom/PressAnnouncements/ucm473505.htm>.

Intranasal naloxone administration has been effectively completed by lay people who complete brief training generally led by non-medical trained professionals⁷. Depot naloxone injections, as well as an oral formulation (naltrexone) are used throughout the US as ongoing treatments to promote sobriety among individuals with substance use disorders⁸. Opioid antagonism can induce withdrawal symptoms that are well documented in the literature, such as nausea, sweating, and jitteriness. Associations between the endogenous opioid system and neural factors underlying eating behavior are well-documented⁹⁻¹².

The Diagnostic and Statistical Manual (DSM) of Mental Disorders – 5th edition outlines criteria for substance dependence, and several self-report measures have been constructed to diagnose substance use disorders. In the past 10 years, researchers have proposed and begun to investigate food addiction by considering food as other researchers have considered other substances (i.e., illicit drugs, alcohol^{13,14}). Food addiction has been proposed as a phenotype in obesity^{15,16}, and more than 30% of treatment-seeking individuals with obesity endorse compulsive overeating^{17,18}, defined as the consumption of large amounts of food whilst feeling out of control over one's eating.

The endogenous opioidergic system, specifically, μ -opioid activity, plays a critical role in the neural experience of reward that follows from eating highly palatable food^{9,19}, especially foods high in sugars^{10,20,21}. Eating these foods acutely stimulates the release of endogenous opioids, which, in turn, promotes further eating. Chronic overeating of these highly palatable and possibly addictive foods²¹⁻²³ can alter μ -opioid activity in ways that increase susceptibility to, and intensify experiences of, food cravings²⁴⁻²⁷. In short-term experimental studies, rats chronically consuming a highly palatable diet that are then either removed from this diet or administered an μ -opioid antagonist display opioid-withdrawal behavior¹⁰. Animal studies also show that administration of a μ -opioid antagonist decreases short-term ingestion of highly palatable, sweet food, even using doses of a μ -opioid antagonist that do not impact intake of standard chow^{21,28}. One phase II placebo-controlled 24-week study ($N = 138$) of intranasal naloxone for binge eating disorder has been reported in abstract form at the American Psychiatric Association's 166th annual meeting, but has not been published²⁹. It involved intranasal naloxone (2 mg) (or intranasal placebo) before binge eating up to 2 times daily (up to 4 mg intranasal naloxone total daily). Eighty-one percent of subjects completed the trial, and there were no serious adverse events. Results indicated that naloxone, relative to placebo, resulted in less time spent binge eating and greater weight loss from weeks 12 to 24. This trial was registered at clinicaltrials.gov (NCT01567670).

We have published data showing that overweight and obese women who report nausea (a common opioid withdrawal symptom³⁰) following ingestion of a standard 50 mg dose of the μ -opioid antagonist naltrexone³¹ also report greater emotional, reward-driven, and/or binge eating^{1,2,32}. Thus, antagonizing the endogenous opioid system is a promising method

by which to test for altered μ -opioid activity related to problematic overeating that does not require expensive imaging procedures. The method that my colleagues and I at UCSF have used involves oral naltrexone³¹, which requires several hours of data collection due to a slower mechanism of action. Utilizing intravenous administration, while rapid, would pose additional subject burden and discomfort, as it involves injection by needle. Using intranasally administered naloxone, which is now used clinically throughout the US and is has been fast-tracked for FDA approval for drug overdose, would dramatically reduce subject burden (reduces study period from 4 hours to less than 1 hour), and would obviate the use of needles.

1.1 Overview of Non-Clinical Studies

Naloxone Hydrochloride Injection Package Insert: See [Appendix A](#).

From Package Insert: Carcinogenesis, Mutagenesis, and Impairment of Fertility

Studies in animals to assess the carcinogenic potential of naloxone hydrochloride have not been conducted. Naloxone hydrochloride was weakly positive in the Ames mutagenicity and in the in vitro human lymphocyte chromosome aberration test but was negative in the in vitro Chinese hamster V79 cell HGPRT mutagenicity assay and in the in vivo rat bone marrow chromosome aberration study. Reproduction studies conducted in mice and rats at doses 4-times and 8-times, respectively, the dose of a 50 kg human given 10 mg/ day (when based on surface area or mg/m²), demonstrated no embryotoxic or teratogenic effects due to naloxone hydrochloride.

From Package Insert: Use in Pregnancy

Teratogenic Effects: Pregnancy Category C: Teratology studies conducted in mice and rats at doses 4-times and 8-times, respectively, the dose of a 50 kg human given 10 mg/day (when based on surface area or mg/m²), demonstrated no embryotoxic or teratogenic effects due to naloxone hydrochloride. There are, however, no adequate and well-controlled studies in pregnant women. Because animal reproduction studies are not always predictive of human response, naloxone hydrochloride should be used during pregnancy only if clearly needed.

1.2 Overview of Clinical Studies

From Package Insert: Pharmacokinetics: Distribution, Metabolism, and Elimination

Following parenteral administration, naloxone is distributed in the body and readily crosses the placenta. Plasma protein binding occurs but is relatively weak. Plasma albumin is the major binding constituent, but significant binding of naloxone also occurs to plasma constituents other than albumin. It is not known whether naloxone is excreted into human milk. Naloxone hydrochloride is metabolized in the liver, primarily by glucuronide conjugation with naloxone-3-glucuronide as the major metabolite. In one study the serum half-life in adults ranged from 30 to 81 minutes (mean 64 ± 12 minutes). In a neonatal study the mean plasma half-life was observed to be 3.1 ± 0.5 hours. After an oral or intravenous dose, about 25-40% of the drug is excreted as metabolites in urine within 6 hours, about 50% in 24 hours, and 60-70% in 72 hours.

[figure not shown]
From Package Inserts: Clinical Pharmacology

Naloxone hydrochloride prevents or reverses the effects of opioids including respiratory depression, sedation, and hypotension. It can also reverse the psychotomimetic and dysphoric effects of agonist-antagonists such as pentazocine. Naloxone hydrochloride is an essentially pure opioid antagonist, i.e., it does not possess the “agonistic” or morphine-like properties characteristic of other opioid antagonists. When administered in usual doses and in the absence of opioids or agonistic effects of other opioid antagonists, it exhibits essentially no pharmacologic activity. Naloxone hydrochloride has not been shown to produce tolerance or cause physical or psychological dependence. In the presence of physical dependence on opioids, naloxone hydrochloride will produce withdrawal symptoms. However, in the presence of opioid dependence, opiate withdrawal symptoms may appear within minutes of naloxone hydrochloride administration and subside in about 2 hours. The severity and duration of the withdrawal syndrome are related to the dose of naloxone hydrochloride and to the degree and type of opioid dependence.

From Published Research: Route of Administration

Recent research indicates that intranasal administration (IN) is similar in effectiveness to IM delivery in reversing opioid (heroin) overdose³³. IN administration is considered an effective option in the treatment of overdose when IV administration is impossible or undesirable⁵. Animal data indicate that the peak plasma levels following intranasal delivery occurs within 3 minutes of administration³⁴.

Figure 1. Structure of naloxone hydrochloride.

2 STUDY RATIONALE

More than 30% of individuals who are overweight or obese and seeking treatment for weight loss endorse problems with binge-like, compulsive overeating^{17,18}. A large body of research has documented overlaps between the endogenous opioid system and eating behavior⁹⁻¹², and in the past decade, food addiction has been proposed as a phenotype in obesity^{15,16}. Data show that women are more sensitive to exogenous opioidergic blockade, as defined by experiencing nausea and other withdrawal-like effects more often than men^{35,36}.

We have published data showing that overweight and obese women who report nausea (a common opioid withdrawal symptom³⁰) following ingestion of a standard 50 mg dose of the μ -opioid antagonist naltrexone³¹ also report greater emotional, reward-driven, and/or

binge eating^{1,2,32}. Our studies have found that women who endorsed nausea responses following naltrexone ingestion had larger reductions in self-reported overeating and greater weight loss when assigned to a weight loss intervention with mindful eating training rather than when assigned to a standard weight loss intervention. Both studies^{1,2}, however, used oral administration (naltrexone), which required three hours of observation to capture data from the time period involving peak response³¹. Thus, antagonizing the endogenous opioid system is a promising method by which to test for altered μ -opioid activity related to problematic overeating.

Intranasal naloxone has been shown to achieve peak plasma levels in 3 minutes in rodents³⁴. Although IV administration would reduce the amount of time needed, this would add a needle stick and therefore increase subject burden. Hence, to (1) reduce the amount of time needed to investigate associations between eating behavior, obesity, and the endogenous opioid system, thereby reducing subject burden, and (2) take the initial steps toward the development of a cost- and time-effective method to assess endogenous opioid activity in women, we plan to evaluate the use of naloxone hydrochloride administered intranasally (intranasal naloxone). This study will provide important preliminary data for future studies investigating treatment matching for weight loss interventions. The development of an intranasal naloxone protocol may contribute to the identification of individuals who may benefit from the incorporation of intervention components traditionally used in substance misuse treatment (e.g., opioid misuse) into their weight-loss intervention program.

2.1 Risk / Benefit Assessment

The most significant potential benefit of this study is to contribute to the development of an inexpensive, non-invasive method for assessing endogenous opioidergic activity in obesity. This study will generate key preliminary data for investigating this method, which may prove useful in identifying individuals with obesity who engage in binge-like, compulsive overeating (“opioid-mediated eating”) that requires treatment modalities traditionally used to treat substance dependence disorders.

Intranasal Naloxone-related risks

Intranasal naloxone is known to reverse (and is used for the purpose of reversing) opioid overdose and can reverse the analgesic effects of an opioid analgesic being taken chronically (e.g., for pain)^{4-6,37}. Intranasal naloxone has minimal drug interaction potential⁵. Intranasal naloxone is not used as a continuous medication and is used in acute situations involving overdose, meaning that individuals receiving intranasal naloxone are not tested for the use of other medications prior to receiving it. See [Appendix A](#) for package insert.

3 STUDY OBJECTIVES

3.1 Primary Objective

1. To determine if 2 mg/2 mL intranasal naloxone (1 mg/1 mL per nostril) elicits the withdrawal symptom of nausea (present versus absent) in obese women (compared to intranasal placebo).

3.2 Secondary Objectives

1. To determine if 2 mg/2 mL intranasal naloxone (1 mg/1 mL per nostril) elicits other withdrawal symptoms, as measured by subjective opiate withdrawal scales³ in obese women (compared to intranasal placebo).
2. To determine the rate of the salivary cortisol response following intranasal naloxone administration in obese women (compared to intranasal placebo).

4 STUDY DESIGN

4.1 Study Overview

This is a single center, double-blind, placebo-controlled, randomized, crossover trial that will include 24 subjects. Subjects will be in the study for up to 3 weeks. Total time involved will be approximately 5-6 hours. There will be a period of at least 24 hours between study Visits 1 and 2.

4.2 Total Study Duration:

Total duration of subject participation will be up to 3 weeks, with one session of web-based screening, one session involving a telephone screening call to confirm eligibility and introduce the subject to the study and two lab sessions involving administration of test and control products (first lab session includes urine screen). Total duration of the study, including recruitment and subject study completion, is expected to be 6 months.

5 CRITERIA FOR EVALUATION

5.1 Primary Efficacy Endpoint

Presence or absence of the self-reported withdrawal symptom of nausea following administration of test product (intranasal naloxone) versus following administration of the control product (intranasal placebo). We will assess for presence of nausea (before and) following administration of each the test and the control products.

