8.2 Blinding

Due to the objectives of the study, the identity of the test product and control product will be unknown to investigators, study staff, and subjects, excepting two study staff, who will prepare study syringes (see **8.4.3 Preparation of Study Syringes**). The following study procedures will be in place to ensure double-blind administration of the test product and control product:

Access to the randomization table will be strictly controlled and available only to the UCSF Research Pharmacy staff who create it and the two unblinded study staff who will prepare study syringes at each subject visit.

The study blind will be broken on completion of the clinical study and after the study database has been locked.

During the study, the blind may be broken **only** in emergencies when knowledge of the subject's condition (control or test product) is necessary for further subject management. When possible, the Investigator will discuss the emergency with the Medical Monitor, [name], prior to unblinding.

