15.2 Demographic and Baseline Characteristics

The following demographic variables at screening will be summarized: race, age, height and weight.

153 Analysis of Primary Endpoint

McNemar's tests will be performed to evaluate whether there is a statistically significant difference in nausea response (dichotomously scored as present or absent) across the test product (intranasal naloxone) and control product (intranasal placebo) conditions.

154 Analysis of Secondary Endpoints

Linear mixed effects regression modeling will be performed to assess differences across conditions in rate of cortisol change over the course of all assessments (baseline and 20 and 50 minutes post-administration).

155 Sample Size and Randomization

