We do not expect any nausea responses to the control product. Under the null hypothesis of no difference between conditions, we would also expect no nausea responses under the alternative. In terms of probability, "no responses" implies a probability of 0: In other words, an impossible event. A single nausea response to intranasal naloxone would decisively refute the null. But nausea responses, under either condition, are not literally impossible. We have therefore powered against the expected value of 0 by using the beta distribution with $r = 0$ as a Bayesian prior, in place of the usual point value. The beta with $r = 0$ is a U-shaped distribution concentrating most of the density on the extreme values. Specifically, for values of p from .01 to .99, in .01 increments, we calculated the ordinate of the beta distribution with trial values of N ; calculated the one-tailed rejection region (outcomes of fewer than 0 nausea responses were not considered) for that value of p and N ; calculated the power for that N and an alternative value of p (e.g., .4); then used the corresponding ordinate for each value of p as a weight, and calculated the average across the range from .01 to .99 as our estimate of power. Since nausea responses are not literally impossible, we also explored power with null proportions up to .3, with the alternatives in the below table. For these nonzero values, a standard binomial power analysis would have sufficed, but for consistency we have used the corresponding Bayesian priors. The beta prior with $r = N/10$, for example, will concentrate probability on values near .1, whereas that with $r = 0$ will concentrate it around 0. The latter, approximating the impossible event, of course yields high power, whereas power declines as the binomial becomes more symmetrical. For the values of potential interest to us, an N of 24 will suffice for 80%+ power. (Following from the above rationale, the entries in the table below do not correspond to standard power calculations for the McNemar test. The test for 0% vs. 40%, for example, is a test of whether the percentages for the two populations are both 20%; the power of this test is just 1 of 99 values averaged, with weights from the beta distribution, for the results in the table below).

% Endorsing Nausea		Number Needed (N)	Power to detect difference
Control Product	Test Product		
0%	20%	20	.811
0%	30%	12	.823
0%	40%	9	.844
10%	40%	16	.817

20%	50%	21	.805
30%	60%	24	.805

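### Does the primary McNemar test lack a usable definition of a nausea response, given two ratings after each product?

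*Combined protocol and SAP*

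**What the plan says.** The Synopsis (Efficacy Evaluations) lists "Self-reported nausea at 0 minutes (pre-administration), and 10 and 30 minutes following administration of test product or control product", and Section 10 repeats these times and states that each rating is present versus absent. Section 5.1 makes the primary endpoint "Presence or absence of the self-reported withdrawal symptom of nausea following administration of test product (intranasal naloxone", against the same after placebo, and adds: "We will assess for presence of nausea (before and) following administration of each the test and the control products". Section 3.1 asks whether naloxone elicits nausea, present versus absent.

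Section 15.3 says that McNemar's "tests will be performed to evaluate whether there is a statistically significant difference in nausea response" across the two products. It gives no test version, alpha or sidedness. The only sidedness in the documents is the one-tailed rejection region of the power calculation in Section 15.5. The table there has one "Endorsing Nausea" percentage per product and is introduced with "For the values of potential interest to us, an N of 24 will suffice for 80%+ power". Section 15.5 also says that its entries are not standard McNemar power. On control nausea it states: "We do not expect any nausea responses to the control product". Section 8.2 fixes the time of unblinding: "The study blind will be broken on completion of the clinical study and after the study database has been locked".

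**The concern.** McNemar's test takes one yes/no per woman per product, and each visit supplies two post-dose values. A response could mean nausea at 10 minutes, at 30 minutes, at either or at both. The pre-dose rating has no stated role, and nothing says how to score a visit with one rating missing. The plural 'tests' in 15.3 could be taken to mean one test per time point.

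With 24 women, such choices could decide the result. If every discordant pair favours naloxone, the uncorrected chi-square needs 4 pairs, the exact one-sided test 5 and the exact two-sided test 6. A rule chosen after unblinding could be chosen for its result, and the table's rates carry no label saying which rule they describe.

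**Working it through.** **1. The plan's own figures.** Inputs are from 15.5. For each p = .01 to .99, take the one-tailed binomial rejection region for N at alpha .05 (assumed), compute power at the naloxone rate, and average with Beta(r, N − r) weights, where r = N × control rate (r near 0 for 0%).

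| Control / naloxone | N | Stated | Recomputed |
|---|---|---|---|
| 0 / 20% | 20 | .811 | .811 |
| 0 / 30% | 12 | .823 | .823 |
| 0 / 40% | 9 | .844 | .844 |
| 10 / 40% | 16 | .817 | .817 |
| 20 / 50% | 21 | .805 | .805 |
| 30 / 60% | 24 | .805 | .805 |

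All six rows reproduce without a combining rule. The percentages are hypothetical response rates, so the calculation can be checked as it stands. Only the label is missing.

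**2. What the text supports.** Nausea is present following administration if it is reported at either rating after the spray. Requiring it at both times would score a woman nauseated at 10 minutes and recovered by 30 as 'absent', which does not fit 'presence' or 'elicits'. No section singles out 10 or 30 minutes. Section 15.3 pairs its plural with one singular difference across two conditions and mentions no testing by time.

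**3. Is the single comparison valid in either common version?** Let m be the response rate under both products, with visits independent. Each discordant type then has probability m(1 − m): .09, .16 and .21 at m = 10%, 20% and 30%. Enumerating the trinomial with N = 24, two-sided alpha .05 (assumed), gives these false-positive rates:

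| Version | m = 10% | 20% | 30% |
|---|---|---|---|
| Exact | .006 | .018 | .023 |
| Uncorrected chi-square | .046 | .044 | .042 |

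Both stay below .05, so validity does not turn on the version.

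**4. Power by rule.** Take 40% as the either-time rate and control nausea as 0%. Let s be the share of nauseated women nauseated at both times (not given in the documents), with the two times equally affected. The response rate is .40 for either, .40 × (1 + s)/2 for one time and .40 × s for both. At s = .50 these are .40, .30 and .20. All discordant pairs favour naloxone, so power is P(Bin(24, rate) ≥ k), with k = 6 for exact two-sided (2 × .5^6 = .031), k = 5 for exact one-sided (.5^5 = .031) and k = 4 for uncorrected chi-square (p = .0455).

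| Version | Either | One time | Both |
|---|---|---|---|
| Exact two-sided | .960 | .771 | .344 |
| Exact one-sided | .987 | .889 | .540 |
| Uncorrected chi-square | .997 | .958 | .736 |

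At s = .25 and .75, exact two-sided power is .578 and .896 for one time, .028 and .771 for both. At s = 1 the rules coincide.

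The spread depends on the anchor. If 40% is instead the rate at one time, with s = .50, the either-time rate is .40/.75 = .533 and the both-times rate is .267. Exact two-sided power is then .960 for one time, .999 for either and .649 for both. With 0% control nausea, 'either' never has the lowest power, because its naloxone rate is at least that of the other rules.

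**5. If a test were run at each time.** Treating the times as independent, the chance of at least one false positive is 1 − (1 − size)². At 10%, 20% and 30% nausea this is .012, .036 and .045 for exact tests, .012, .036 and .044 with the continuity correction, and .090, .087 and .083 uncorrected. At 5% nausea the uncorrected figure is .037. At the 0% control nausea that the plan expects, with no effect, there are no responses and no inflation.

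**The case for a change.** The strongest case for a change is that no section records the either-time rule or requires it to be fixed before the blind is broken. A reader cannot exclude that several readings will be tried. Choosing the best of four (10 minutes, 30 minutes, either, both) gives a false-positive rate of .105 to .131 with uncorrected chi-square and .019 to .064 with exact tests, over assumed nausea of 10% to 30% and within-visit correlation of .3 to .8. With 0% control nausea, a 40% either-time rate, s = .50 and the exact two-sided test, the women needed for 80% power are 19 (either), 25 (one time) and 39 (both), so 24 suffices under only one rule.

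Part of this stands: the rule, test version, alpha and sidedness are unwritten. The harm, however, needs a departure from the natural reading, and the inflation also needs uncorrected tests and appreciable control nausea. The 25 exceeds the plan by one woman and is two-sided; in the one-tailed direction used for the power calculation, 21 suffice. No rule would rescue the 10% versus 40% row: it has only .547 under the exact two-sided test even as an either-time rate with independent visits. That gap comes from the one-sample power calculation, which 15.5 itself separates from McNemar power.

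The pre-dose rating does not need a role for validity. Women eat from the buffet before both products and the order is randomised, so background nausea arises under both and the placebo comparison accounts for it. A missing 10- or 30-minute rating is possible, but both fall within one supervised visit of 1.5 to 2 hours.

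**Conclusion.** The concern does not call for a change. The plan leaves a definition unwritten, but its wording points to one response, nausea at 10 or 30 minutes, and to one comparison between products. That analysis has a false-positive rate of at most .046 in the settings checked, in either version, and power of .960 (exact two-sided) on the 0% versus 40% row. Requiring the exact version would gain nothing for this comparison: the uncorrected version already holds its size at 10% to 30% nausea and has more power.

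These figures assume N = 24, alpha .05 and independent visits; the power figure also takes 40% as the either-time rate and 0% control nausea. The conclusion would differ if separate uncorrected tests by time, each allowed to count, were actually planned. Nothing in the documents says so.
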